8.7.5 Method of Detecting AEs and SAEs

Care will be taken not to introduce bias when detecting AEs and/or SAEs. Open-ended and non-leading verbal questioning of the participant is the preferred method to inquire about AE occurrences.

8.7.6 Recording and Follow-Up of AE and/or SAE

8.7.6.1 AE and SAE Recording

When an AE/SAE occurs, it is the responsibility of the investigator to review all documentation (e.g., hospital progress notes, laboratory reports, and diagnostics reports) related to the event.

- The investigator will then record all relevant AE/SAE information.
- It is not acceptable for the investigator to send photocopies of the participant's medical records in lieu of completion of the required form.
- There may be instances when copies of medical records for certain cases are requested by the sponsor, RA, or EC. In this case, all participant identifiers, with the exception of the participant number, will be redacted on the copies of the medical records before submission.
- The investigator will attempt to establish a diagnosis of the event based on signs, symptoms, and/or other clinical information. Whenever possible, the diagnosis (not the individual signs/symptoms) will be documented as the AE/SAE.

8.7.6.2 Assessment of Severity

The investigator will make an assessment of severity for each AE and SAE reported during the study and assign it to one of the following categories:

- **Mild:** No limitation in normal daily activity.
- **Moderate:** Some limitation in normal daily activity.
- **Severe:** Unable to perform normal daily activity.

8.7.6.3 Assessment of Causality

The investigator is obligated to assess the relationship between study intervention and each occurrence of each AE/SAE. The investigator will use clinical judgment to determine the relationship. The relationship of study treatment to an AE will be determined by the investigator based on the following definitions:

1. “Not Related”: The AE is not related if exposure to the investigational product has not occurred, or the occurrence of the AE is not reasonably related in time, or the AE is considered unlikely to be related to use of the investigational product, i.e., there are no facts, evidence, or arguments to suggest a causal relationship, or the AE is more likely related to the subject’s pre-existing condition.
2. “Related”: The administration of the investigational product and AE are considered reasonably related in time and the investigational product is more likely than other causes to be responsible for the AE or is the most likely cause of the AE. A reasonable possibility of a relationship conveys that there are facts, evidence, and/or arguments to suggest a causal relationship, rather than a relationship cannot be ruled out.

The causality assessment is one of the criteria used when determining regulatory reporting requirements.

- Alternative causes, such as underlying disease(s), concomitant therapy, and other risk factors, as well as the temporal relationship of the event to study intervention administration, will be considered and investigated.
- The investigator will also consult the IB and/or product information, for marketed products, in their assessment.
- For each AE/SAE, the investigator **must** document in the medical notes that they have reviewed the AE/SAE and has provided an assessment of causality.
- Following an initial report, the investigator may change their opinion of causality in light of follow-up information and send an SAE follow-up report with the updated causality assessment.

8.7.6.4 Further Evaluation and Follow-up of AEs and SAEs

The investigator is obligated to perform or arrange for the conduct of supplemental measurements and/or evaluations as medically indicated or as requested by the sponsor to elucidate the nature and/or causality of the AE or SAE as fully as possible. This may include additional laboratory tests or investigations, histopathological examinations, or consultation with other health care professionals.

- If a participant dies during participation in the study or during a recognized follow-up period, the investigator will provide the sponsor with a copy of any postmortem findings including histopathology.
- New or updated information will be recorded in the originally submitted documents.
- The investigator will submit any updated SAE data to the sponsor within 24 hours of receipt of the information.

After the initial AE/SAE report, the investigator is required to proactively follow each participant at subsequent visits/contacts. All SAEs and AESIs will be followed until resolution, stabilization, the event is otherwise explained, or the participant is lost to follow-up, as defined in [Section 7.3 Lost to Follow-up](#).

8.7.7 Reporting of SAEs

8.7.7.1 SAE Reporting via Paper Data Collection Tool

- Email transmission of the electronic SAE Form (paper data collection tool) is the preferred method to transmit this information to the Medical Monitor or study CRA. A scanned copy of a printed SAE form may be accepted if the electronic form cannot be submitted.
- In rare circumstances and in the absence of email equipment, notification by telephone is acceptable with a copy of the SAE Form sent by overnight mail or courier service.
- Initial notification via telephone does not replace the need for the investigator to complete and sign the SAE Form within the designated reporting timeframes.
- Contacts for SAE reporting can be found on the title page of this document (the Medical Monitor) or in the sponsor contact list provided separately.

8.7.8 Regulatory Reporting Requirements for SAEs

- Prompt notification by the investigator to the sponsor of an SAE is essential so that legal obligations and ethical responsibilities towards the safety of participants and the safety of a study intervention under clinical investigation are met.
- The sponsor has a legal responsibility to notify both the local regulatory authority and other regulatory agencies about the safety of a study intervention under clinical investigation. The sponsor will comply with country-specific regulatory requirements relating to safety reporting to the regulatory authority, institutional review boards (IRBs)/independent ethics committees (IECs), and investigators.
- An investigator who receives an investigator safety report describing an SAE or other specific safety information (e.g., summary or listing of SAEs) from the sponsor will review and then file it along with the IB and notify the IRB/IEC, if appropriate according to local requirements.

8.7.9 Pregnancy

- Details of all pregnancies in participants will be collected after the start of study intervention and until the participant's final visit.
- If a pregnancy is reported, the investigator will record pregnancy information on the appropriate form and submit it to the sponsor within 24 hours of learning of the pregnancy.

- While pregnancy itself is not considered to be an AE or SAE, any pregnancy complication or elective termination of a pregnancy for medical reasons will be reported as an AE or SAE.
- Abnormal pregnancy outcomes (e.g., spontaneous abortion, fetal death, stillbirth, congenital anomalies, ectopic pregnancy) are considered SAEs and will be reported as such.
- The participant will be followed to determine the outcome of the pregnancy. The investigator will collect follow-up information on the participant and the neonate and the information will be forwarded to the sponsor.
- Any poststudy pregnancy-related SAE considered reasonably related to the study intervention by the investigator will be reported to the sponsor as described in [Section 8.7.8 Regulatory Reporting Requirements for SAEs](#). While the investigator is not obligated to actively seek this information in former study participants, they may learn of an SAE through spontaneous reporting.

Any participant who becomes pregnant while participating in the study will not undergo any additional MDMA-assisted therapy sessions, though in some cases may continue participation in non-drug therapy sessions. Prior to continuation of non-drug study interventions following pregnancy, the following must occur:

- The sponsor and the relevant IRB/IEC give written approval.
- The participant gives signed informed consent.
- The investigator agrees to monitor the outcome of the pregnancy and the status of the participant and her offspring.

8.7.10 Disease-related Events

The following disease-related events (DREs) are common in participants with PTSD and can be serious/life threatening:

- Self-injurious behavior associated with suicidal ideation
- Suicidal ideation scores of 4 or 5 on the C-SSRS
- Suicidal ideation judged to be serious or severe in the opinion of the investigator

These events involve the exacerbation of a chronic or intermittent pre-existing condition, including either an increase in frequency and/or intensity of the condition that would normally be appropriately recorded as AEs/AESIs. Because these events are associated with the disease under study, they would typically not be reported in an expedited manner to RA/ECs ahead of the annual reporting as part of the DSUR according to standard guidance for expedited reporting.

However, if any of the following conditions applies, then the event must be recorded as an AE/SAE (instead of a DRE) and reported in an expedited manner as appropriate:

1. The event is, in the investigator's opinion, of greater intensity, frequency, or duration than expected for the individual participant.
2. The investigator considers that there is a reasonable possibility that the event was related to study intervention.
3. The applicable RA/EC has requested expedited reporting of these DREs.

Note: The FDA has requested that the current clinical development program submit expedited reports for these DREs related to suicidality. Therefore, these DREs reported in this protocol *will*

be reported to the FDA in an expedited manner as described in [Section 8.7.3 Adverse Events of Special Interest](#).

8.7.11 Interruptions and Arrangements Due to COVID-19 Pandemic or Any Other Unforeseen Emergency at Clinic Locations

This clinical trial may be impacted by the Coronavirus Disease 2019 (COVID-19) global pandemic. Special arrangements may be required for study continuation and participant and study site staff safety due to this or any other unforeseen emergency in the future. The following accommodations in the protocol will be allowed, captured, and noted in the Clinical Study Report as COVID-19 deviations when applicable:

- Integrative Sessions may be conducted by tele-assessment.
- Delaying the start of medication tapering after enrollment and the subsequent Treatment Period per [Section 6.8.1 Psychiatric Medications](#).
- Delaying Experimental Sessions and associated Integrative Sessions.
- Delaying IR assessments for participants who cannot complete them remotely off-site.
- Use of prohibited medications and/or cannabis or initiation of new therapy for participants with significant study delays, which will be reviewed by the study team before each Experimental Session and re-tapered prior to resuming treatment per [Section 6.8 Concomitant Therapy](#).

For any participant with COVID-19 related illness, continued trial participation after full recovery of the disease may be appropriate after discussion between the site physicians and Medical Monitors on a case-by-case basis.

8.8 Other Assessments

8.8.1 Pharmacokinetics

PK parameters are not evaluated in this study.

8.8.2 Genetics

Genetics are not evaluated in this study.

8.8.3 Biomarkers

Biomarkers are not evaluated in this study.

8.8.4 Immunogenicity Assessments

Immunogenicity is not evaluated in this study.

8.8.5 Medical Resource Utilization and Health Economics

For all participants throughout the study, the investigator and study site personnel will collect data about health care resource utilization associated with medical encounters.

The data collected will:

- Include the reasons and duration of hospitalizations and emergency room visits.
- Exclude procedures, tests, and encounters mandated by the protocol.

The sponsor may use the collected data to conduct economic analyses.

9.0 Statistical Considerations

The Statistical Analysis Plan (SAP) will be finalized prior to database lock and it will include a more technical and detailed description of the statistical analyses described in this section. This section is a summary of the planned statistical analyses of the most important endpoints including primary and key secondary endpoints.

9.1 Statistical Hypotheses

No formal hypothesis testing will be conducted.

9.2 Analysis Sets

For the purposes of analysis, the following analysis sets are defined:

Participant Analysis Set	Description
Full analysis set (FAS)	
• All enrolled participants.
mITT	
• All participants who receive IMP in at least one Experimental Session and have at least one follow-up assessment.
Safety analysis set	
• All participants who are exposed to study intervention.

9.3 Statistical Analyses

9.3.1 General Considerations

Data will be summarized to provide descriptive information on safety, tolerability, and effectiveness. Descriptive and summary statistics will be performed, as appropriate. Statistics will include number of observations, mean, standard deviation, median, range, and inter-quartile range for continuous variables, and the number and percent for categorical variables; 95% or 90% confidence intervals will be presented where appropriate. Additional statistics such as geometric mean and coefficient of variation (CV%) may be calculated as warranted. Demographics and baseline characteristics (e.g., age, sex, race, ethnicity, body weight) will be summarized using descriptive statistics.

The reasons for all discontinuations will be tabulated and grouped by treatment group and major reason. All deviations related to study inclusion or exclusion criteria, conduct of the study, subject management, or subject assessment will be described.

9.3.2 Primary Endpoint Analysis

The primary endpoint is the change in mean CAPS-5 Total Severity Scores from Baseline to Primary Outcome Visit. Analysis of the primary endpoint will be conducted using a ANCOVA model with change from baseline score as the outcome and baseline CAPS-5 score as an independent variable. Adjustment for additional potential covariates will be explored. Additional details will be provided in the SAP.

9.3.3 Secondary Endpoint Analysis

The key secondary endpoint is the change in mean SDS score from Baseline to Primary Outcome Visit.

Analysis of the secondary and exploratory outcomes will be conducted in the same manner as the primary efficacy analysis. Adjustment for potential covariates will be explored.

9.3.4 Exploratory Endpoints Analyses

An exploratory responder analysis will characterize clinical significance of PTSD treatment effect from Baseline to Primary Outcome Visit based on the following categories:

- **Treatment Response:** 10-point or greater reduction in CAPS-5 Total Severity Score.
- **Loss of Diagnosis:** 10-point or greater reduction in CAPS-5 Total Severity Score and no longer meeting PTSD diagnostic criteria on CAPS-5.
- **Remission:** CAPS-5 Total Severity Score of under threshold or less and no longer meeting PTSD diagnostic criteria on CAPS-5.

Exploratory sub-group analyses may be conducted when possible to evaluate effectiveness by treatment group and individual demographic characteristics (e.g., age, gender, ethnicity, index trauma, dissociative subtype of PTSD, presence of secondary traumatic stressors during the assessment period with LEC-5, diagnosis of comorbid depression, diagnosis of comorbid psychiatric diagnosis, group cohort, and number of Experimental Sessions completed). Exploratory analyses of secondary outcome measures will be described in the Statistical Analysis Plan.

9.3.5 Safety Analyses

AEs: AEs will be mapped to preferred term and system organ class using the most up to date Medical Dictionary for Regulatory Activities. AEs that begin after the first administration of study drug or existing AEs that worsen after the first dose of study medication are considered Treatment Emergent AEs (TEAEs). The number and percentage of participants reporting TEAEs will be summarized by system organ class and preferred term, by severity, and by relationship to study drug. The number and percentage of participants with SAEs, and the number and percentage of participants with AEs leading to treatment discontinuation will also be summarized by MedDRA system organ class and preferred term. Clinically significant changes in physical examination, laboratory parameters, vital signs, ECG, psychiatric health, withdrawal, and suicidality will be reported as AEs.

Concomitant medications: Concomitant medications will be coded using WHO Drug Dictionary and will be classified by Anatomical Therapeutic Chemical classification level 4 and preferred term for the Safety Analysis Set. Frequencies and percentages of participants using will be presented. All medication use will be listed regardless of the timing of the start of the medication.

Vital signs: Vital signs will be summarized using descriptive statistics of actual values and changes from baseline over time. The incidence of clinically notable vital signs will be summarized. Continuous laboratory data will be examined for trends using descriptive statistics of actual values and changes from baseline over time. These data will also be categorized as low, normal, or high based on the reference ranges of the central laboratory. Shift tables from baseline to each post baseline time point will be presented.

Suicidality: For each subject, C-SSRS data will be categorized into (1) suicidal ideation (nonspecific, method but no intent or plan, method and intent but no plan and method, intent and plan) and (2) suicidal behavior (suicide attempt, interrupted attempt, aborted attempt and preparatory acts and non-suicidal self-injurious behavior) at each visit. An increase in suicidality (i.e., passive suicidal ideation defined as an onset of suicidal ideation or behavior, or active suicidal behavior defined as an escalation from suicidal ideation to suicidal behavior) in a subject will be reported as an AE. The percentage of participants with passive suicidal ideation and active suicidal behavior will be presented by visit.

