Assess incidence of AESIs, defined as AEs specified in the protocol related to cardiac function, suicidality, and abuse liability.	All visits following enrollment	AEs reported in eCRF
Assess incidence of SAEs.	All visits	SAEs reported in eCRF
Assess incidence of psychiatric concomitant medications taken.	Phone and Site Screening, all visits with exception of Preparatory Session 1 and (Outcome)	Medication review
Assess relative incidence of positive or serious ideation and suicidal behavior.	All site visits	C-SSRS
Assess mean changes in physiological measures.	Site Screening, Experimental Session 1 and Experimental Session 2 (pre-IMP administration and end of visit)	Blood pressure, heart rate, and body temperature
Exploratory		
Evaluate group cohesion within and between cohorts based on comparison of PTSD treatment outcome.	CAPS-5 (Baseline) and (Outcome)	CAPS-5
Assess changes in severity of dissociative symptoms associated with PTSD.	DSP-1 (Baseline (Outcome)	DSP-I
Evaluate the effect of adverse childhood experiences on PTSD treatment outcome as a covariate.	Preparatory Session 3 & Safety review, (Baseline), and (Outcome)	ACE CAPS-5
Characterization of PTSD severity with a descriptive time course plot.	Preparatory Session 3 & Safety review, , Integrative Session 1.4, and (Outcome)	PCL-5

Objectives	Assessment Window	Endpoints
Assess changes in severity of dissociative symptoms associated with PTSD treatment outcome.	CAPS-5 T1 (Baseline) and CAPS-5 T2 (Outcome)	DSP-I
Assess changes in group cohesion.	Preparatory Session 3 & Safety review, Integrative Session 1.4, Integrative Session 2.4, and Study Termination	GQ
Assess changes in depression symptoms.	Preparatory Session 3 & Safety review and Study Termination	BDI-II
Assess changes in attachment dynamics.	Preparatory Session 3 & Safety review and Study Termination	ECR-S
Assess changes in positive outcomes following trauma.	Preparatory Session 3 & Safety review and Study Termination	PTGI
Assess changes in perceived social support.	Preparatory Session 3 & Safety review and Study Termination	SPS
Assess changes in self-compassion.	Preparatory Session 3 & Safety review and Study Termination	SCS
Assess changes in health economics.	Preparatory Session 3 & Safety review and Study Termination	CSI
Assess changes in quality of life.	Preparatory Session 3 & Safety review and Study Termination	EQ-5D-5L
Assess changes in workplace productivity.	Preparatory Session 3 & Safety review and Study Termination	HPQSF

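### The derived C-SSRS labels in Section 9.3.5 can count a first suicidal behaviour as passive ideation and leave worsening within ideation uncounted

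*Protocol*

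**What the plan says.** The Suicidality paragraph of Protocol Section 9.3.5 works in two steps.

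**Step 1, categories at each visit.** C-SSRS data are sorted into suicidal ideation ("nonspecific, method but no intent or plan, method and intent but no plan and method, intent and plan") and suicidal behaviour, a list of attempt types that ends with "preparatory acts and non-suicidal self-injurious behavior". No condition on earlier ideation applies here.

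**Step 2, derived labels.** An increase in suicidality is then defined, introduced by i.e., through two cases only: "passive suicidal ideation defined as an onset of suicidal ideation or behavior, or active suicidal behavior defined as an escalation from suicidal ideation" to behaviour.

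An increase so defined is to be reported as an AE, and the labels feed the planned table: "The percentage of participants with passive suicidal ideation and active suicidal behavior will be presented by visit".

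The safety objective that the C-SSRS serves, in the Synopsis (Section 1.1), is "Assess relative incidence of positive or serious ideation and suicidal behavior". Section 8.7.10 names "Suicidal ideation scores of 4 or 5 on the C-SSRS" among the disease-related events.

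**The concern.** The two derived labels do not follow the events that they are named for. The passive-ideation label admits behaviour. The active-behaviour label requires that ideation came first. Neither admits a participant who already has ideation and gets worse without reaching behaviour.

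This matters because suicidality is both a safety objective and an AESI in this trial. The protocol says that ideation is common in PTSD (Section 8.6.1) and that C-SSRS scores rose during preparatory sessions in earlier trials (Section 2.3.1, Table 1). Participants who enter with ideation are therefore to be expected, and the labels are least informative for them. The trial is open-label, has at most 18 participants and has no data monitoring committee, so a reader of the report is likely to take the by-visit percentages at face value.

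**Working it through.** The plan has no figure to reproduce on this point. The check applies the stated definitions to every possible upward move.

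**Inputs.** Six ordered states: none, the four ideation levels listed in Section 9.3.5, and behaviour. The maximum N is 18 (Section 1.1, Overall Design).

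**Number of upward moves.** 6 × 5 / 2 = 15, made up of:

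- none to an ideation level: 4
- none to behaviour: 1
- one ideation level to a higher one: 4 × 3 / 2 = 6
- ideation to behaviour: 4

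**Two readings of onset.** Strict: onset means arising from neither ideation nor behaviour. Literal: any first ideation or first behaviour is an onset.

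| Move | Count | Strict reading | Literal reading |
|---|---|---|---|
| none to ideation | 4 | passive | passive |
| none to behaviour | 1 | passive only | passive only |
| ideation to higher ideation | 6 | neither | neither |
| ideation to behaviour | 4 | active | passive and active |

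On both readings, 1 of 15 moves carries a label of the wrong kind and 6 of 15 carry none. On the literal reading a further 4 carry both, so the labels are not mutually exclusive. These are counts of possible moves, not of expected events. With five ideation levels, as the scores in Section 8.7.10 suggest, the uncounted moves would be 5 × 4 / 2 = 10 of 7 × 6 / 2 = 21. The pattern is the same.

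**Weight of one participant.** 1/18 = 5.6 percentage points, or 1/15 = 6.7 if, as an assumption, 15 are evaluable. Example: one of 18 participants attempts suicide with no earlier recorded ideation and nobody else changes. The table shows active behaviour 0/18 = 0% and passive ideation 1/18 = 5.6%. Labelled by the event, behaviour is 5.6%.

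**How likely is any affected case?** The documents give no rate. If each of 18 participants independently had probability p of an affected move, the chance of at least one is 1 − (1 − p)^18:

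| Assumed p | Chance of at least one |
|---|---|
| 1% | 16.5% |
| 2% | 30.5% |
| 5% | 60.3% |
| 10% | 85.0% |

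These values of p are illustrative. Independence is also an assumption, since participants are treated in groups.

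**The definition of an increase beside the other sections.**

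- Section 8.7.1.1 makes an exacerbation of a pre-existing condition, in frequency or intensity, an AE.
- The AE paragraph of Section 9.3.5 makes clinically significant changes in suicidality AEs.
- Section 8.7.3 lists suicide attempts, and ideation that the investigator judges serious or severe, as AESIs.
- Section 8.7.10 treats ideation scores of 4 or 5 as an exacerbation that would normally be recorded as an AE or AESI, and sends these events to the FDA on an expedited basis.

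Under these sections worsening within ideation can be a reportable event. Under the two-case definition it is not an increase at all.

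**The case against.** The strongest reply is that the defect is confined to one derived table. Step 1 of the same paragraph files a suicide attempt under behaviour and keeps the ideation level at every visit, so a correct table can always be rebuilt. Serious events have other routes: an attempt is an AESI, and a rise from a score of 2 to 5 is caught by Section 8.7.10. The trial is a feasibility study with no hypothesis tests. Most of this stands, and it limits both the scope and the severity of the point.

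A reader might infer more than the document supports:

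- **That the percentages will be wrong.** They are distorted only if an affected move occurs.
- **That serious events in general go to the mildest label.** This is certain only for a first behaviour without recorded ideation. Behaviour after ideation does reach the active label.
- **That worsening goes unreported.** The two-case definition says which increases become AEs. It does not bar others, and the sections set out above can capture them. Below a score of 4, however, that capture rests largely on the investigator's judgement.
- **That the non-suicidal self-injury item and the four listed levels are equally serious.** The first is mainly table layout. On the second, the protocol does not define the individual scores, so which level is absent cannot be settled from it.

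What the reply does not answer is that the labels are stated in the protocol and are not left to the SAP. Reporting an event elsewhere does not change a percentage that is computed from the wrong label.

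**Conclusion.** The point holds as a wording defect with a real but conditional effect. The derived labels can understate suicidal behaviour, can count one person under both labels, and omit worsening within ideation. Each affected participant moves a reported percentage by 5.6 points at N = 18. The total effect cannot be sized without an event rate. The summary built on these labels also has no entry for serious ideation, which the safety objective names.

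The conclusion rests on reading i.e. as introducing a complete list and on the tabulated labels being the ones just defined. Both are the plain reading. Severity is should-fix: the underlying data are retained and event reporting has other routes, but an SAP that follows the protocol text would carry the fault into the report.

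**What to change.** Reword the Suicidality paragraph of Section 9.3.5, and carry the same wording into the SAP before database lock:

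1. Assign labels by the event itself. Any suicidal behaviour counts as behaviour whether or not ideation came first, and any ideation counts as ideation.
2. Add a category for worsening within ideation against a stated reference. Show change from study entry and also change from the last pre-dose assessment. A single pre-dose reference could absorb a rise during the preparatory period and hide it.
3. Report serious ideation (C-SSRS 4 or 5, as in Section 8.7.10) as its own entry, to match the Synopsis objective, and state which listed level corresponds to which score.
4. Reconcile the definition of an increase with Sections 8.7.1.1, 8.7.3 and 8.7.10 and with the AE paragraph of 9.3.5, so that the protocol gives one answer on which changes count.

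A separate row for non-suicidal self-injury would be a minor tidy-up.

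The cost is small. The C-SSRS is already administered at preparatory sessions, before and at the end of each Experimental Session, and at the follow-up calls, so no new data are needed. Item 4 may touch Section 8.7 as well as 9.3.5, and a protocol amendment needs IRB/IEC approval under Appendix 1.
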